### 3.3 Sample Size Considerations

This study has been sized making the following assumptions:

- Inferential testing is at the (two-sided) 5% level, and with a desired power of 80%.
- The primary endpoint is the difference between treatment groups in change from baseline WOMAC Pain (average of 5 pain items) at 12 weeks post-dose, as measured using a 0-10 scale
- The standard deviation of the endpoint is 2.2, as assessed from review of similar studies from clinicaltrials.gov
- The desired difference to detect is 0.8.

Based on these assumptions, a sample size of approximately 120 subjects per treatment group is required. Assuming a drop-out rate of approximately 20%, 150 subjects will be randomized and dosed in each treatment arm.

### 3.4 Analysis Populations

Evaluation of the primary and secondary efficacy endpoints will be performed using the Intention-to-Treat (ITT) Population. In addition, if the Per-protocol Set (PPS) Population markedly differs from the ITT population, as discussed in Section 3.7, identical analyses for the PPS population will be performed for the primary and key secondary endpoints. Safety endpoints will be analyzed using the Safety Population. Pharmacokinetic (PK) data will be analyzed using the Safety Population.

#### 3.4.1 Intention-to-Treat Population

The intention-to-treat (ITT) population consists of all subjects who are both randomized to and receive treatment. Analysis will be conducted allocating subjects to the treatment to which they were randomized, irrespective of what was actually received.

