6. RANDOMIZATION, BLINDING AND UNBLINDING

6.1 Randomization

At Screening Visit 1a subjects will be assigned a unique subject identification (ID) number that will be used throughout the study. The Investigator will maintain a list of subject ID numbers and names to enable records to be found at a later date.

Randomization will take place at Visit 2, before IMP administration. Randomization will be performed centrally, based on a pre-defined computer-generated randomization list accessed via an interactive response technology (IRT) system. The IRT system will ensure random allocation of eligible subjects in a 1:1 ratio to EP-104IAR 25 mg or vehicle treatment groups.

A statistician otherwise not involved in the trial will generate the randomization scheme. The randomization list will not be available to any person involved in the conduct and evaluation of the trial until the trial database is declared clean and locked.

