7.2.2 Dosing and Administration Guidelines

Following randomization, unblinded site staff will prepare and administer the injection according to the instructions provided in the IMP Handling Manual. The injection procedure will be performed by a suitably qualified and experienced physician, except in Denmark, where other study personnel with documented training and long-term experience in IA injections may also perform the injection. Wherever possible the same unblinded injector should administer the drug to all subjects at the site.

To maintain subject blinding to treatment assignment, the subject's view must be shielded to ensure they cannot see the dosing procedure or the filled syringe.

The syringe containing the constituted EP-104IAR or vehicle control should be labeled with the subject number, date and time of dosing.

Knee Preparation

The Index knee will be prepared with chlorhexidine or betadyne per the site's standard injection protocol. Lidocaine (also known as lignocaine) may be administered prior to the injection procedure to make the procedure more comfortable. Lidocaine may be injected into subcutaneous tissues along the needle pathway but may not be injected into the suprapatellar bursal space.

Joint Aspiration

Prior to dose administration the unblinded injector will aspirate the subject's knee. The volume of effusion (if any) will be recorded in the eCRF. If it is not possible to extract any synovial fluid this should be noted in the eCRF.

Ultrasound Guidance

Sites are required to administer the injection using ultrasound guidance.

Knee Position

The needle will be inserted via the medial or lateral route with the subject's knee in an extended (non-flexed) position and the entire contents of the syringe (5 mL) should be administered into the synovial space using a 21-gauge 1.5-inch needle (provided by the Sponsor).

Post Administration

A sterile dressing will be applied after the injection is completed, and the subject will be observed for 5 minutes to ensure that they tolerated the injection.

Empty used vials of drug and vehicle and the syringe used for injection will be placed into a residual drug kit container (provided by the Sponsor). The used needles should be discarded according to usual practice. This container will be stored as described in the IMP Handling Manual until drug accountability has been performed by the unblinded Monitor.

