11.3 Populations

11.3.1 Intention-to-Treat Population

The intention-to-treat (ITT) population consists of all subjects who are randomized to treatment. Analysis will be conducted allocating subjects to the treatment to which they were randomized, irrespective of what was actually received.

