## 5. DEVIATIONS FROM THE PROTOCOL

The Full Analysis Set (FAS) Population is defined in the protocol but is omitted from this document, as it is not used for any of the analyses.

Two additional exploratory efficacy endpoints are included in this document but are not in the protocol:

- Difference between treatment groups in patient beliefs about treatment received
- Difference between treatment groups in physician beliefs about treatment received.

Three additional secondary efficacy analyses were added whereby WOMAC Pain responder levels (30, 50, 70) are summarized at Weeks 12, 18 and 24.

The analyses of perceptions of treatment received/administered are expanded to consider summaries by response type.

The intention-to-treat (ITT) population definition is updated to all subjects who are both randomized to and receive treatment. Analysis will be conducted allocating subjects to the treatment to which they were randomized, irrespective of what was actually received.

	EP-104IAR-201 Statistical Analysis Plan	Version: Final 1.0
	Date: 14-Jun-2023	Page 38 of 38

An MRI sub-study population was added as a study population to reflect the sub-study for the imaging.

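### The SAP's ITT set leaves out randomised subjects who were not dosed; this affects the OMERACT-OARSI strict-responder analyses, not the primary model

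*SAP*

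**What the plan says.** **Protocol.** Section 11.3.1 says the ITT population "consists of all subjects who are randomized to treatment", analysed by assigned arm. Section 11.7.1 names this population for the primary endpoint. A separate full analysis set in 11.3.2 requires dosing and at least one post-baseline assessment.

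**SAP.** Section 3.4.1 defines ITT as "all subjects who are both randomized to and receive treatment", still analysed by assigned arm. Section 3.4 gives the set its role: "Evaluation of the primary and secondary efficacy endpoints will be performed using the Intention-to-Treat (ITT) Population". Section 5 lists the new definition among the deviations from the protocol, with no rationale, and drops the full analysis set as unused.

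**Order of events and blinding.** Protocol 6.1: "Randomization will take place at Visit 2, before IMP administration". Protocol 7.2.2: "Following randomization, unblinded site staff will prepare and administer the injection". The same section has the unblinded injector aspirate the knee before the dose. Protocol 6.3 gives users with unblinded roles in the IRT system the allocation of every randomised subject at their site. Protocol 5.4 foresees subjects who are randomised but never dosed, and does not replace them.

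**Responder rule.** SAP 3.8.1 compares Week 12 OMERACT-OARSI strict responders with Fisher's exact test and counts anyone who discontinues before Week 12 as a non-responder. SAP 3.8.2 applies the same analysis at Weeks 4, 8, 16, 20 and 24.

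**The concern.** Leaving out undosed subjects is usually harmless when the reason for not dosing cannot depend on the arm. Here that cannot be taken for granted. Between randomisation and injection, the people handling the subject know the allocation. The work also differs by arm: the active product is a powder suspended in vehicle immediately before injection (Protocol 7.1.1), whereas the control is vehicle alone (7.1.2). Protocol 10.2.8 foresees constitution and administration errors. Non-dosing could therefore differ by arm without any intent.

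A set whose membership depends on a step after randomisation, carried out by people who know the arm, lacks the protection that the name ITT implies. With the full analysis set dropped and ITT narrowed, the SAP has no efficacy set of all randomised subjects. What is at stake is the strict-responder comparison, the last of the four key secondary endpoints in the formal hierarchy. There, a subject who would count as a failure under the protocol's definition leaves the denominator.

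**Working it through.** **1. Planned numbers.** SAP 3.3 assumes SD 2.2, difference 0.8, two-sided 5% and 80% power. The normal approximation gives 119 per arm and the t-test version 119.7, so the stated 120 reproduces; 120 / 0.80 = 150 randomised per arm. Neither ITT definition alters this calculation. The 150 is used below as the denominator.

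**2. Which analyses depend on the definition?**

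- *Primary MMRM (SAP 3.7).* It is fitted to change from baseline at each post-dose week with no imputation. SAP 4.1 counts WOMAC weeks from dosing, so an undosed subject has no analysis week and contributes no row. The estimate is essentially the same under either definition.
- *Multiple imputation (SAP 3.7).* Data missing for reasons other than lack of efficacy are imputed on the basis of the treatment actually received, with models run by randomised arm. An undosed active-arm subject brought into this step would be given EP-104IAR-like outcomes without having been injected.
- *OMERACT-OARSI strict responders (SAP 3.8.1, 3.8.2).* Leavers are failures. An undosed leaver is in the denominator as a failure under the protocol's set and missing under the SAP's. This is where the definition matters.
- *WOMAC Pain 30/50/70% responders (SAP 3.8.2).* These are reported with the number of subjects with data, and no non-responder rule is stated, so this mechanism does not arise.

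**3. Size for strict responders.** The documents give neither the number undosed nor a responder rate. Assume a rate of 45% among the dosed and k of 150 undosed in one arm, all non-responders:

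rate over all randomised = 0.45 × (150 − k) / 150

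| k (assumed) | Dosed | Rate, all randomised | Drop from 45% |
|---|---|---|---|
| 0 | 150 | 45.0% | 0 |
| 3 | 147 | 44.1% | 0.9 points |
| 5 | 145 | 43.5% | 1.5 points |
| 8 | 142 | 42.6% | 2.4 points |

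**4. Could this change a test result?** Only near the threshold. Assume 75 active and 58 vehicle responders, two-sided Fisher's exact test:

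| Comparison | p |
|---|---|
| All randomised: 75/150 vs 58/150 | 0.063 |
| 3 undosed dropped, active arm only: 75/147 vs 58/150 | 0.036 |
| 5 undosed dropped, active arm only: 75/145 vs 58/150 | 0.027 |
| 3 undosed dropped in each arm: 75/147 vs 58/147 | 0.061 |

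With 58 vehicle responders and three undosed in the active arm only, the result crosses 5% at just two active counts. At 74, p is 0.081 over all randomised and 0.048 with the three dropped; at 75, it is 0.063 and 0.036. At 73 neither analysis is significant (0.103 and 0.062), and at 76 both are (0.048 and 0.027). The example shows that a change is possible, not that it is likely.

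**The case against.** **A reader might infer that the unblinded injector chooses whether to dose. The documents do not support this.** They assign the injector preparation, aspiration and injection, with no decision on whether to proceed. Eligibility review and Index-knee selection come before randomisation (Protocol 9.1.4, 9.2.4.1), and the right to withdraw a subject lies with the investigator and the sponsor (5.4). This objection stands. What remains is that the step is carried out by people who know the arm, so dependence on arm is possible.

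**A reader might infer that the change is concealed or that undosed subjects go unreported.** Neither is so. SAP section 5 states the change, Protocol 11.1 requires the SAP to be final before unblinding, and subjects are still analysed as assigned. SAP 3.5 tabulates the number randomised and the number in each set by treatment, so the undosed count follows by subtraction. Withdrawal reasons are also summarised by treatment. Only an explicit row for undosed subjects, with the reasons for not dosing, is missing.

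**A reader might infer that the primary result is biased, or that every analysis should go back to all randomised.** The primary model is essentially the same either way. Under the present rule, adding undosed subjects to the multiple imputation would make it worse.

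**The size is hypothetical.** This is right: both the responder rate and the undosed counts are assumed, all non-dosing is placed in one arm, and strict response is tested formally only if the primary and three other key secondary endpoints succeed. This limits the importance of the point but does not remove it.

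**Conclusion.** The point holds in a limited form. The SAP uses the name ITT for a randomised-and-dosed set, departs from the protocol's definition without a reason, and does so in a trial where those who carry out the injection know the allocation. The analyses affected are the OMERACT-OARSI strict-responder comparisons. On the assumptions used (45% rate, 3 to 8 of 150 undosed in one arm, all undosed counted as failures), the shift is 0.9 to 2.4 percentage points in that arm. If nobody went undosed, there is no effect. The sample size is unchanged and the primary MMRM essentially so. The documents do not show that non-dosing did, or will, differ by arm. The severity is low: a cheap improvement, not a threat to the trial's main conclusion.

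**What to change.** 1. Analyse the OMERACT-OARSI strict-responder endpoints (Week 12 and the other listed weeks) in all randomised subjects as Protocol 11.3.1 defines them. State that undosed subjects count as non-responders; the rule has to be explicit because SAP 4.1 gives them no analysis week.
2. Where the SAP's set is kept, including the MMRM and the multiple imputation, call it 'modified ITT', and give the reason for the change in SAP section 5.
3. Add a row to the SAP 3.5 disposition table for subjects randomised but not dosed, with reasons, by arm.
4. Do not extend the multiple imputation to undosed subjects under its present rule, which would treat undosed active-arm subjects as if they had been injected.

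The cost is some SAP wording, a changed denominator in the strict-responder tables and one disposition row. No new data on outcomes are needed. The downside is that responder rates may come out slightly lower.

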#### 3.4.2 Per-protocol Set Population

The per-protocol analysis set (PPS) population consists of all randomized subjects who received a dose of randomized treatment, had at least 1 post-baseline assessment, and had no major protocol violations potentially impactful of efficacy data. The subjects in this group will be analyzed based on the treatment they received.

	EP-104IAR-201 Statistical Analysis Plan	Version: Final 1.0
	Date: 14-Jun-2023	Page 16 of 38

Major protocol violations leading to exclusion from the per-protocol set population will be finalized after the blind review process and will be documented in a memo prior to unblinding of treatment assignments and database lock. All protocol deviations will be listed by subject.

### **3.4.3 Safety Population**

The safety population consists of all randomized subjects who were administered a dose of IMP/vehicle control. The subjects in this group will be analyzed based on the treatment they received.

### **3.4.4 MRI Sub-Study Population**

The MRI sub-study consists of all randomized subjects who entered into the exploratory imaging sub-study. The subjects in this group will be analyzed based on the treatment they received.

## **3.5 Subject Disposition**

The number of subjects screened will be summarized overall and by site. The number of subjects randomized and included within each of the analysis sets will be summarized by treatment, site, and overall, where applicable.

The number and percentage of subjects who completed the study will be presented by treatment and overall, for each of the analysis populations. Frequency and percentage of subjects who withdrew or discontinued from the study, and the primary reason for withdrawal, will also be summarized by treatment and overall.

## **3.6 Subject Accounting and Baseline Characteristics**

Demographic data and subject characteristics at Baseline will be summarized descriptively. Medical history, detailed OA history and Knee OA Criteria (including duration of symptoms in the index knee in years and time since diagnosis in the index knee in years, where each is defined as the number of days from the date of symptom onset or diagnosis to the date of dosing divided by 365.25) will be summarized.

Dose administration details, exposure and compliance with IMP, characterized by; volume of synovial fluid collected prior to injection, lidocaine injection, knee of injection, route of injection, injected suspension volume, residual amount of FP in the injection kit, and actual dose of FP administered, will be summarized descriptively. Incidence of prior and concomitant medications and procedures will be summarized by WHO Drug dictionary coded terms – Anatomical

 PROSOFT Clinical	EP-104IAR-201 Statistical Analysis Plan	Version: Final 1.0
	Date: 14-Jun-2023	Page 17 of 38

Therapeutic Chemical (ATC) classification and preferred name (PN). Prior and concomitant medications/procedures are classified as follows.

- A prior medication/procedure is any medication/procedure that started prior to date of the dose of study drug. Medications with an unknown start date will also be considered prior medications.
- A concomitant medication/procedure is any medication/procedure used on or after the date of the dose of study drug. Ongoing medications/procedures or medications/procedures with an unknown end date will also be considered concomitant medications.

A medication/procedure may be classified as both prior and concomitant.

### 3.7 Primary Endpoint Analysis

The primary efficacy endpoint is the difference in change from baseline between EP-104IAR and vehicle in WOMAC Pain at Week 12, in the ITT population. Baseline WOMAC Pain will be calculated at the individual level and is defined as the average of no more than three pre-dose measurements including the three scheduled measurements: 2 measurements during the Washout and Baseline Period and 1 at Visit 2 (pre-dose). If the subject has less than three pre-dose measurements, the average of all available pre-dose measurements will serve as the subject's baseline value. If a subject has more than three pre-dose measurements, then the three measurements collected immediately prior to pre-dose will be used to derive baseline WOMAC pain and earlier measurements will not contribute.

Change from individual pre-dose baseline will then be calculated for each post-dosing weekly assessment from Week 1 through Week 24. A mixed-effects model for repeated measures (MMRM) model will then be fit to the change from baseline data for all subjects in the ITT population, including fixed effects terms for: site (potentially grouped, see Section 4.2 for more details); individual baseline WOMAC Pain; and the treatment-by-week interaction, where treatment and week are both defined as categorical variables. A random per-patient intercept will also be included. An unstructured covariance matrix at the patient level will initially be fit; if this model fails to converge numerically, a compound symmetry structure will be used.

No imputation of missing data will be performed for this analysis; the MMRM model allows handling of missing data under the assumption that data is missing at random (MAR). To assess robustness to the assumption that data is missing at random, a multiple imputation approach will be used. Under this approach, outcome data will be imputed according to the following logic:

	EP-104IAR-201 Statistical Analysis Plan	Version: Final 1.0
	Date: 14-Jun-2023	Page 18 of 38

- If missing data is due to lack of efficacy (as captured by the Study Termination page on eCRF), data will be imputed as if subjects received placebo.
- If missing data is due to other reasons, data will be imputed as if subjects received their actual treatment.

The imputation procedure will begin by generating 100 imputed datasets with SEED=1867004294, excluding subjects that discontinued due to lack of efficacy. The 100 imputed datasets for the WOMAC Pain scores will be generated separately for each randomized treatment with a fully conditional specification (FCS) model using the regression method. Following these initial imputations, 100 copies of the non-missing WOMAC Pain scores for subjects that discontinued due to lack of efficacy will be generated. One of these copies will be added to each of the 100 imputed datasets generated for the placebo group. A single imputation will then be generated for each of these 100 combined sets of data using the same FCS model as above. This will result in 100 imputed datasets for all subjects.

Change from baseline to Week 12 in WOMAC Pain from each of the 100 imputed datasets will be analyzed separately using an ANCOVA model with effects treatment, site (possibly grouped; see Section 4.2) and baseline WOMAC Pain. For each comparison of interest, estimates and their associated standard errors from the ANCOVA models will be combined to produce a single overall estimate and standard error. Associated confidence intervals and p-values will then be generated as appropriate.

The SAS® MI procedure will be utilized for imputing data. The first imputation step is described above.

The imputation step for subjects randomized to EP-104IAR that discontinued due to lack of efficacy will be similar to the step above except with SEED=454120304, NIMPUTE=1, and without “by trt” since imputation will be based on a single treatment group.

The results of the 100 analyses will be transformed into a normal statistic and combined into a single analysis using PROC MIANALYZE.

In addition to the robustness analysis described above, if the PPS population markedly differs from the ITT population, identical analyses for the PPS population will be performed. Subject to finalization after the blind review, the PPS population will be considered significantly different if it is less than 85% of the ITT population.

	EP-104IAR-201 Statistical Analysis Plan	Version: Final 1.0
	Date: 14-Jun-2023	Page 19 of 38

